8.5.2 Exclusion Criteria

If any of the following apply, the patient **MUST NOT** enter the trial:

1. *(Exclusion criterion removed in Amendment 3)*
2. Presence of CTCAE (Common Terminology Criteria for Adverse Events) grade ≥ 2 peripheral neuropathy.
3. Clinically significant active viral, bacterial or fungal infection requiring:
 - Intravenous treatment with anti-infective therapy that has been administered less than two weeks prior to first dose in this trial, or
 - Oral treatment with anti-infective therapy that has been administered less than one week prior to first dose in this trial.
 - Prophylactic anti-infective therapy, which is given without clinical symptoms is allowed.
4. Ongoing acute or chronic inflammatory skin disease.
5. Women who are breast feeding.

Pregnant women must not take part in this trial and will be considered as screening failures.

8.5.3 Discontinuation Criteria

8.5.3.1 Discontinuation of Trial Treatment

A patient's trial treatment should be discontinued if:

- The investigator believes that for safety reasons (e.g., unacceptable toxicity) it is in the best interest of the patient to discontinue trial treatment.
- Any unacceptable toxicities as defined in Section 9.5.
- The patient becomes pregnant.
- Disease progression.

- The patient (or the patient's representative) withdraws consent for administration of trial drug.
- The patient is unable to adhere to the trial visit schedule or comply with protocol requirements.
- The patient received concurrent (non-protocol) anti-cancer therapy or any other investigational agent.
- The patient receives exclusionary medication as described in Section 9.6.1.

8.5.3.2 Discontinuation from the Trial

The sponsor will make every effort to ensure patients are followed up for completion of safety assessment in the trial. Patients will be withdrawn from the trial for the following reasons:

- Trial medication is withdrawn
- Withdrawal of consent
- Lost to follow-up
- Death
- Sponsor terminates the trial

If a patient withdraws from the trial, an EOT Visit should be performed, preferably 30 days after last treatment.

When a patient withdraws consent for trial participation before completing the trial, the reason for withdrawal is to be documented in the electronic case report form (eCRF) and in the source document.

8.5.3.3 Lost to Follow-Up

A patient will be considered lost to follow-up if he or she repeatedly fails to return for scheduled visits and is unable to be contacted by the trial site.

The following actions must be taken if a patient fails to return to the clinic for a required trial visit:

- The site must attempt to contact the patient and reschedule the missed visit as soon as possible and counsel the patient on the importance of maintaining the assigned visit schedule and ascertain whether or not the patient wishes to and/or should continue in the trial.
- In cases in which the patient is deemed lost to follow-up, the investigator or designee must make every effort to regain contact with the patient (where possible, three telephone calls and, if necessary, a certified letter to the patient's last known mailing address or local equivalent methods). These contact attempts should be documented in the patient's medical record.

8.5.4 Screen Failures

Screen failures are defined as patients who consent to participate in the clinical trial but are not subsequently entered in the trial. Only information about demography, reason for screen failure including eligibility criteria not met, and any SAEs will be collected.

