8. INVESTIGATIONAL PLAN

8.1 Overall Trial Design and Plan

This is an open-label, multicenter trial to collect long-term safety and efficacy data and to provide ongoing access to tisotumab vedotin for patients with solid tumors who have completed a tisotumab vedotin base trial. Patients demonstrating clinical benefit but who have been withdrawn from the base tisotumab vedotin trials for reasons that are not considered critical and unmanageable for the safety of the patient (as evaluated by the investigator and the sponsor) can also enter this protocol. For patients who received tisotumab vedotin as a single-agent in the base trial, tisotumab vedotin will be given according to the dosing level and schedule administered in the base trial at the time of exiting. Reduced dose can be administered in accordance with the mitigation strategies (Section 9.4 to 9.5.6) or at the discretion of the treating physician based on individual patient observed toxicity profile and after consultation and agreement by the Genmab Medical Officer. Patients will be treated with the tisotumab vedotin dosing regimen followed by the patient in the base trial, until the investigator determines that the patient is no longer benefitting from treatment (i.e., disease progression or unacceptable toxicity has occurred), the trial is terminated by the sponsor, the patient withdraws consent, or for other reasons as defined in this protocol.

In the Treatment Phase, investigators will monitor and assess the patients for response to treatment and for disease progression. Timing and assessments are outlined in the Schedule of Activities (Table 1). Any SAEs, non-serious grade ≥ 2 ocular AEs, non-serious grade ≥ 3 AEs, overdose and/or medication errors, and pregnancies should be reported to the Safety CRO by trial site personnel within 24 hours of their knowledge of the event. All (S)AEs should be reported from the time the patient has signed the ICF until the End-of-Trial (EOT) Visit, or until the patient withdraws consent or starts subsequent anti-cancer therapy, whichever occurs first.

An EOT Visit will occur 30 days after the last administration of trial drug. However, if a patient is unable to return to the site at that time or if the patient is scheduled to start subsequent treatment, this visit should be performed as soon as possible after the last administration of trial drug.

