8.2 Schedule of Activities

Table 1: Trial Flow Chart - 1Q3W Treatment Scheme

Procedure	Screening (up to 21 days before Day 1)	Treatment Period Cycle 1 – X (21-day cycle \pm 7 days) Day 1	End-of-Trial Visit (30 days after last dose + 1 week)	Comments
Informed consent	X			
Eligibility criteria	X			
Demography	X			
Height	X			
Weight	X	X		To be taken at screening and at start of each treatment cycle
Pregnancy test	X	X		To be taken at screening and at start of each treatment cycle for women of childbearing potential
Vital signs	X	X		Blood pressure pulse, heart rate and temperature taken at screening and before and after treatment
ECG	X	X		To be taken at screening and before each treatment
ECOG performance status	X			
Neuropathy assessment	X			
Skin assessment	X			
Ophthalmology evaluation	X	X	X	To be performed according to the schedule in the base protocol. Patients experiencing ocular symptoms must be referred to an ophthalmologist for prompt review (preferably within 72 hours and no later than within 1 week).
Laboratory sampling	X	X	X	Local laboratories will be used. Screening laboratory samples do not need to be repeated if performed at the base trial. Details on laboratory samples are provided in Section 10.3.4.

Procedure	Screening (up to 21 days before Day 1)	Treatment Period Cycle 1 – X (21-day cycle \pm 7 days) Day 1	End-of-Trial Visit (30 days after last dose + 1 week)	Comments
Trial drug administration		X		Treatment administration schedule to follow the treatment schedule in the base protocol.
Preventive eye therapy		X		Preventive eye therapy to be administered in relation to infusions as detailed in Section 9.5.4.
Response assessment (CT-scan, PSA, CA 125)	X	X	X	Last CT-scan of base trial to be used at screening if less than 4 weeks old, otherwise a new CT-scan needs to be obtained. Then, to be performed every 6 weeks (at the end of every second cycle) during Treatment Period, and response to be confirmed 4 weeks later. Response assessments will be recorded in the eCRF. PSA will be performed for CRPC patients. CA 125 will be performed for patients with ovarian cancer.
Radionuclide bone scan		X		For patients with CRPC, assessment of bone metastases by radionuclide bone scan every 12 weeks is recommended, but frequency should be based on local standards. If there is suspicion of progression, another bone scan will be performed twelve weeks later.
AE/SAE review	X	X	X	
Concomitant medication	X	X	X	

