11.2 Adverse Event Reporting

The investigator must report all directly observed AEs and all AEs reported by the patient. A general type of question should be used similar to “Do you have any health problems?” or “Have you had any health problems since your last visit?”

All AEs must be reported from the time the patient signs the ICF until 30 days after the last dose of tisotumab vedotin, or until the patient withdraws consent or starts subsequent anti-cancer therapy, whichever occurs first.

Any AE (signs, symptoms and diagnosis) occurring prior to signing the ICF must be recorded in the applicable base protocol eCRF.

Registration of Adverse Events in the eCRF:

- All AEs must be recorded in the eCRF.
- Grade 3 and 4 abnormal laboratory test results must be reported as AEs when these are assessed as clinically significant by the reporting investigator.

Reporting of Adverse Events to the Safety CRO:

- All SAEs
- Ocular grade ≥ 2 AEs
- All non-serious grade ≥ 3 AEs
- All events of overdose and/or medication errors, independent of intensity, must be reported as AEs to the Safety CRO.
- Any event of pregnancy must be reported as an AE to the Safety CRO.

Please refer to Section 11.5 for an overview of AE reporting timelines.

All deaths (including deaths due to disease progression) should be reported as an SAE.

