11.3 Events Requiring Immediate Reporting

11.3.1 Serious Adverse Events, Non-serious Grade ≥ 3 Adverse Events, Non-serious Grade ≥ 2 Ocular Events, Overdose and/or Medication Errors, and Pregnancies

Serious adverse events, non-serious grade ≥ 3 AEs, non-serious grade ≥ 2 ocular AEs, overdose and/or medication errors, and pregnancies must be reported from the investigational site to the Safety CRO no later than 24 hours following (a) the patient visit at which such AE was reported, noted or recognized; or (b) the principal investigator’s or any investigator personnel’s receipt of the test results or other information at, or from which, such development was reported, noted or recognized.

Completed SAE Report Forms, Non-serious Grade 3 Adverse Event Report Forms, Non-serious Grade 2 Ocular Adverse Event Report Forms or Pregnancy Forms must immediately be forwarded to the Safety CRO [REDACTED].

[REDACTED]

If you have access to a secured email, you may forward completed SAEs, non-serious grade 3 AEs, non-serious grade 2 ocular events forms or pregnancy forms to:

[REDACTED]

If you do not have access to a secured email, please forward completed SAEs, non-serious grade 3 AEs, non-serious grade 2 ocular events forms or pregnancy forms to:

[REDACTED]

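### Protocol 8.5.4 limits screen failures to SAEs, contradicting the rules in 8.1, 11.2, Table 1 and 11.3.1 that cover AEs from consent, and does not fit the SAP's Enrolled Population

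*Protocol*

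**What the plan says.** Protocol 8.5.4 defines the group: "Screen failures are defined as patients who consent to participate in the clinical trial but are not subsequently entered in the trial". It then limits their data: "Only information about demography, reason for screen failure including eligibility criteria not met, and any SAEs will be collected".

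The safety sections set a wider rule that starts at consent:

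- Protocol 11.2: "All AEs must be reported from the time the patient signs the ICF until 30 days after the last dose of tisotumab vedotin", with earlier stops if consent is withdrawn or another anti-cancer therapy begins. It adds: "All AEs must be recorded in the eCRF".
- Protocol 11.2, on events before consent: "Any AE (signs, symptoms and diagnosis) occurring prior to signing the ICF must be recorded in the applicable base protocol eCRF".
- Protocol 8.1: "All (S)AEs should be reported from the time the patient has signed the ICF until the End-of-Trial (EOT) Visit", with the same two earlier stops.
- Protocol 8.2, Table 1: AE/SAE review is marked in the screening column.
- Protocol 11.3.1: "Serious adverse events, non-serious grade ≥ 3 AEs, non-serious grade ≥ 2 ocular AEs, overdose and/or medication errors, and pregnancies must be reported" to the Safety CRO within 24 hours.

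SAP 4.3.1 defines the Enrolled Population as everyone who signs the consent form, and SAP 4 puts all enrolled patients in the listings. SAP 11.2 adds a flag for AEs that occur before the first dose in this trial.

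**The concern.** In most trials a screen failure has not yet received the study drug, so collecting only SAEs loses little. Here every candidate comes from a tisotumab vedotin base trial, and an event during screening can be toxicity of the drug under study. The primary objective is long-term safety and the primary endpoint is adverse events (Protocol 7). Listings are the only planned output (Protocol 12.2; the SAP allows summary tables only if a need arises). An AE that is not recorded is simply absent from the result.

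Ocular events show the problem best. They are AEs of special interest (Protocol 11.1.3) and the subject of two amendments, but no exclusion criterion in 8.5.2 names ocular toxicity. If a patient develops non-serious conjunctivitis after consent and then fails screening on a laboratory value, 8.5.4 asks for the laboratory reason and not for the conjunctivitis.

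**Working it through.** The plan states no figure on this point, so the check sets the sections side by side. The case is a non-serious AE that starts after consent in a patient who then fails screening.

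| Source | Does it call for the event? | Exception for screen failures? |
|---|---|---|
| Protocol 8.5.4 | No, SAEs only | This is the section specific to them |
| Protocol 8.1 | Yes, all AEs from consent | None stated |
| Protocol 11.2 | Yes, all AEs from consent, in the eCRF | None stated |
| Protocol 8.2, Table 1 | Reviewed at screening | None stated |
| Protocol 11.3.1 | Yes, within 24 hours, if grade ≥ 3 or ocular grade ≥ 2 | None stated |
| SAP 4, 4.3.1 | Patient is enrolled and listed | None stated |

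**Step 1. Can a site satisfy both rules?** No. The opening word of the 8.5.4 sentence makes its list exhaustive, and 11.2 requires more. A site or eCRF designer could reasonably follow 8.5.4 because it is the specific section, or 11.2 because it is the safety section.

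**Step 2. If 8.5.4 is followed, does this protocol send the event elsewhere?** Not clearly. Section 11.2 assigns only pre-consent events to the base-trial eCRF, and 10.1.2 says that no new medical history is taken.

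**Step 3. Does the reason for failure replace the AE record?** Only in part. It would show, for example, that grade ≥ 2 neuropathy was present. It does not call for onset, relatedness, outcome or the grade as an AE, and it misses an event that was not the reason for failing.

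**Step 4. Is the screening period close to dosing?** The documents give no maximum gap since the last base-trial dose. Assume no treatment break. A 21-day cycle with a window of ± 7 days then puts the planned Day 1 of this trial at 21 − 7 = 14 to 21 + 7 = 28 days after the last base-trial dose. Screening precedes Day 1, so it would end within 30 days of that dose. Reuse of base-trial laboratory results up to 21 days old and CT scans up to four weeks old (Protocol 8.5) also suggests a close handover. With a treatment break this need not hold.

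**The case against.** A reader might infer that these events are recorded nowhere, or that the toxicities which stop patients from continuing are the very ones lost. The documents do not support either statement, for these reasons:

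- Section 11.2 requires pre-consent AEs to go in the base-trial eCRF. It does not forbid the base trial from recording later ones. The base protocols are not supplied, so whether GEN701 or GEN702 keeps collecting after consent here is unknown.
- Read literally, 8.1, 11.2 and 11.3.1 still require the events. The finding is a contradiction between sections, and a loss follows only if 8.5.4 is taken to govern.
- Toxicity that causes ineligibility is recorded as the reason for failure and the criteria not met, and the SAP lists both (Listings 16.02.01.01 and 16.02.01.05). Progress notes also record significant observations (Protocol 14.1).
- An event found at screening may have started before consent. Section 11.2 then assigns it to the base-trial eCRF.
- Section 11.4 asks for suspected drug-related SAEs, non-serious grade ≥ 3 AEs and non-serious ocular grade ≥ 2 AEs after participation ends. If it applies to screen failures, which the text does not say, it would catch some later events. It sends them to the Safety CRO, however, and does not clearly put them in the eCRF or the listings.

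A reader might also subtract an assumed consent day from 30 days (consent on day 0 leaves 30 days, on day 21 leaves 30 − 21 = 9) and call the remainder lost observation. That rests on an assumed consent day and measures no loss of events.

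All of these limits stand. None of them removes the conflict, and none supplies a graded AE record in this trial for a site that follows 8.5.4.

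**Conclusion.** The contradiction is established from the text alone. Section 8.5.4 cannot be followed together with 8.1, 11.2 and 11.3.1, and it leaves the SAP listing an enrolled patient whose AE rows may hold SAEs only. The consequence is conditional: where sites follow 8.5.4, non-serious AEs that start between consent and screen failure may not be recorded as graded AEs in this trial.

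The size cannot be computed. The documents give no screen-failure count, no AE rate during screening and no gap since the last base-trial dose. With about 25 patients expected to enter, few patients are likely to be affected, and no effect on the overall safety picture is shown. The point is still worth correcting, because AEs are the primary endpoint, the patients have already been exposed to the drug, and the change is small. That the patients were recently dosed is plausible but assumed. What the base trials collect after consent is unknown.

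**What to change.** 1. In Protocol 8.5.4, replace the SAE item with all AEs from signature of the consent form until the date of screen failure, subject to the stopping rules in 11.2. At minimum, collect SAEs plus the categories in 11.3.1. A longer follow-up that ignores 11.2's stops at consent withdrawal or subsequent anti-cancer therapy should be avoided, because it would hold screen failures to a wider rule than treated patients.
2. Say how 11.2's 30-day limit works for these patients. They receive no dose in this trial, so it can refer only to a base-trial dose.
3. State which eCRF, the base trial's or this trial's, holds AEs after consent in screen failures, so that events are neither lost nor entered twice.
4. In the SAP, add a screen-failure flag to the AE listings (16.02.03.02 to 16.02.03.04 and 16.02.03.06 to 16.02.03.08).

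The cost is a short protocol edit, one SAP sentence and a few extra AE pages for a small, unstated number of screen failures. Treatment is unchanged.

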9. TREATMENT

9.1 Identity of Investigational Medicinal Product

Tisotumab vedotin is presented as a lyophilized powder for reconstitution in water for injection and is intended for dosing by the intravenous route by infusion after dilution in physiological saline solution.

The final composition of the drug product after reconstitution is 10 mg/mL tisotumab vedotin formulated in a mixture of histidine, sucrose and mannitol at pH 6.0.

9.2 Treatment Administered

The investigator must ensure that the trial drug will be used only in accordance with the protocol.

Tisotumab vedotin will be administered as an intravenous infusion on Day 1 of each 21-day cycle (once every three weeks [1Q3W]).

Each patient's dose will be calculated based on the patient's weight (measured at first dosing visit within a cycle) rounded to the nearest kilogram, i.e., assigned dose in mg/kg \times body weight in kg. For patients whose body mass index (BMI) is greater than 30 kg/m², the investigator should use a weight that, based on the patient's height, corresponds to a maximum BMI of 30.

The dose is calculated according to the following formula if BMI is greater than 30 kg/m²:

$$Dose (mg) = x (mg/kg) * 30 (kg/m^2) * height (m) * height (m)$$

Tisotumab vedotin will be administered over a minimum of 30 minutes. If infusion-related events emerge, refer to Section 9.4. The infusion is complete when the infusion line has been flushed with a minimum 15 mL saline. Preventive eye therapy should be administered in relation to infusions as detailed in Section 9.5.4.

Table 2: Trial Treatment Details

	1Q3W Treatment Scheme
Trial Treatment Name:	Tisotumab vedotin
Dosage Formulation:	Vials containing tisotumab vedotin as lyophilized powder for reconstitution
Unit Dose Strength(s)/ Dosage Level(s):	Each vial contains 40 mg of tisotumab vedotin as lyophilized powder to be reconstituted with 4 mL water for injection leading to a 10 mg/mL solution.
Route of Administration:	Intravenous infusion
Dosing Instructions:	2.0 mg/kg or if dose reduced continue the same dose as in base protocol. If patient toxicity profile warrants reduced dose, this can be introduced (see Section 9.5)
Packaging and Labeling:	Trial treatment will be provided in boxes containing 4 vials each. Each box/vial will be labeled as required per country requirement with multi-language labels. Each vial will have a unique vial ID number.

1Q3W=once every 3 weeks

9.3 Preparation/Handling/Storage/Accountability

9.3.1 Trial Treatment Preparation

The dose of tisotumab vedotin for administration must be prepared by the site pharmacy using aseptic technique. Tisotumab vedotin will be supplied to the site pharmacy as bulk supply cartons.

The reconstituted tisotumab vedotin should be diluted into a 0.9% NaCl 100 mL infusion bag according to the dose assigned to the patient.

The infusion must be completed within 24 hours after the tisotumab vedotin vials have been reconstituted. An in-line filter must be used for the infusion. The entire 100 mL infusion volume from the prepared infusion bag needs to be administered, no dead volume is provided.

Please refer to the Preparation and Administration of Tisotumab Vedotin (HuMax-TF-ADC) / IMP Manual for instructions on storage, preparation and infusion. Labeling will be in accordance with the EU Guidelines to Good Manufacturing Practice, Annex 13, Investigational Medicinal Products, and any other applicable local regulatory requirements.

9.3.2 Trial Treatment Storage and Accountability

It is forbidden to use investigational trial drug material for purposes other than as defined in this protocol.

9.3.3 Trial Treatment Storage

Tisotumab vedotin will be stored at 2-8°C in a secure area with restricted access.

9.3.4 Trial Treatment Accountability

The trial drug must exclusively be used for the investigation specified in this protocol and it will only be accessible to authorized staff. The investigator or designee must confirm and document the receipt of the trial drug.

The IMP vials must be kept at the pharmacy. Throughout the trial, all used and unused material will be accounted for on vial ID level in the eCRF. Documented destruction of drugs and containers should be coordinated at the clinical site.

9.4 Treatment of Infusion-Related Reactions

Patients should be monitored during infusion.

- If an infusion-related reaction occurs, the infusion should be interrupted and appropriate medical management instituted. The infusions may be restarted at the investigator's discretion.
- Patients who have experienced prior infusion-related CTCAE grade ≥ 3 reactions in the trial should be pre-medicated before all subsequent infusions with an antihistamine and/or acetaminophen and/or corticosteroid at the investigator's discretion.
- If anaphylaxis occurs, administration of trial drug should be discontinued immediately and permanently, and appropriate medical therapy should be administered.

